## 15.2 Baseline Assessments

The Baseline period is the morning of admission to the study, before dosing. Prospective subjects who meet all eligibility criteria must be admitted to the study in time to give the first dose of study medication at 8 AM ( $\pm 30$  minutes).

The assessments listed below will be performed during the Baseline period before dosing.

- SOWS-Gossop.
- COWS.
- Vital signs (resting [sitting or recumbent, if applicable]) and standing blood pressure and pulse; respiration, temperature) measurements.
- Repeat pregnancy assessment (by “dipstick”), if female.
- Repeat urine drug screen (by “dipstick”).
- Update Inclusion/Exclusion Criteria form to reflect Baseline assessments.
- Update prior medication form to capture any new medications since screening.
- Update complete physical exam form to capture any new physical findings since screening.
- Columbia Suicide Severity Rating Scale (C-SSRS) (Baseline version; [Appendix 5](#)).
- 12-lead ECGs (in duplicate) before the first dose on Day 1 at 8 AM.

## 15.3 Assessments During Treatment

### 15.3.1 Days 1-3 (Mandatory In-clinic)

The assessments or procedures listed below will be performed daily (unless otherwise specified) on Days 1-3 (see Section [15.3.4](#) for assessments/procedures required for discontinuation from the study).

- Study medication administration QID at 8 AM, 1 PM, 6 PM, and 11 PM.

- Effectiveness assessments at estimated time of maximum plasma concentration (Tmax, i.e., 3.5 hours after the first daily dose) including:
  - SOWS-Gossop; and
  - COWS.
- Completion of pre-defined withdrawal treatment goal (e.g., planned detoxification/transition) as assessed by the Principal Investigator (after completion of the SOWS-Gossop and COWS).
- Concomitant medication assessment.
- Vital signs including blood pressure and pulse at rest (sitting [or recumbent if necessary because of an AE]) and standing (if able) before every dose and 3.5 hours after administration of study medication at 8 AM, 1 PM, and 6 PM (7 times per day); respiration and temperature before 8 AM dose only.
- Continuous monitoring for AEs.
- 12-lead ECGs (in duplicate) before the first dose on Day 1 at 8 AM and 3.5 hours ( $\pm 15$  minutes) after dosing.
- A fingerprick blood sample for PK analysis will be collected concurrently with each scheduled ECG.
- Clinical laboratory tests as clinically warranted.
- Complete physical examination 3 to 4 hours after dosing on Day 1 and as clinically warranted.
- C-SSRS (Since Last Visit Version; [Appendix 6](#)) at 3.5 hours after the first dose (8 AM) on Days 1-3.
- A qualitative urine drug screening (by on-site use of “dipsticks”) will be done every day to monitor for contraband.

### 15.3.2 Days 4-7 (In-clinic/Outpatient)

The assessments or procedures listed below will be performed daily (unless otherwise specified) on Days 4-7 (see Section [15.3.4](#) for assessments/procedures required for discontinuation from the study).

- Study medication administration QID at 8 AM, 1 PM, 6 PM, and 11 PM. Note that if subject is receiving outpatient treatment, he/she is required to take a dose of lofexidine in the clinic at each daily clinic visit.
- SOWS-Gossop 3.5 hours after the first daily dose during in-clinic treatment; once daily before an in-clinic dose of lofexidine during outpatient treatment.
- COWS 3.5 hours after the first daily dose during in-clinic treatment; once daily before an in-clinic dose of lofexidine during outpatient treatment.

- Completion of pre-defined withdrawal treatment goal (e.g., planned detoxification/transition) as assessed by the Principal Investigator (after completion of the SOWS-Gossop and COWS).
- Concomitant medication assessment.
- Pill count and review of subject diary ([Appendix 3](#)) to measure compliance with previous day's doses if being treated as an outpatient.
- Vital signs including blood pressure and pulse at rest (sitting [or recumbent if necessary because of an AE]) and standing (if able) during in-clinic treatment before every dose and 3.5 hours after administration of study medication at 8 AM, 1 PM, and 6 PM (7 times per day); respiration and temperature before 8 AM dose only.
- Vital Signs including blood pressure and pulse at rest (sitting [or recumbent if necessary because of an AE]) and standing (if able) during outpatient treatment before an in-clinic dose of lofexidine each day and 3.5 hours after dosing. Note that if the subject cannot stay in the clinic for measurement of the 3.5-hour post-dose vital signs required on Days 4-7, they will be given a portable digital blood pressure machine for measurement of their vital signs at this required time point. Subjects will also be provided a diary ([Appendix 3](#)) to record the measurements along with any symptoms of hypotension and/or bradycardia (see list in Section [13.2.2](#)) the subject may have experienced.
- A fingerprick blood sample will be collected during outpatient treatment when the subject reports to the clinic each day (before next scheduled dose) for analysis of plasma lofexidine concentration to monitor compliance.
- AE assessment.
- Clinical laboratory tests as clinically warranted.
- Complete physical examination as clinically warranted.
- C-SSRS (Since Last Visit Version; [Appendix 6](#)) at 3.5 hours after the first dose (8 AM) during in-clinic treatment; once daily before an in-clinic dose of lofexidine during outpatient treatment.
- Qualitative urine drug screening (by on-site use of “dipsticks”) will be done every day in an in-clinic setting to monitor for contraband and every day in an outpatient setting to monitor for illicit drug use.
- Daily clinic visits and completion of subject diary for outpatients.

Subjects not requiring extended lofexidine treatment can be discharged from the study on Day 7 after receipt of at least one dose of study drug and after all end-of-study procedures have been completed (see Section [15.3.4](#)).

### **15.3.3 Days 8-14 (Outpatient Only)**

Study medication is optional on Days 8-14 for subjects continuing to have withdrawal symptoms per the Principal Investigator's judgment. The assessments and procedures listed

below will be performed daily (unless otherwise specified) (see Section 15.3.4 for assessments/procedures required for discontinuation from the study).

- Daily clinic visits and completion of subject diary.
- SOWS-Gossop before an in-clinic dose of lofexidine.
- COWS before an in-clinic dose of lofexidine.
- Completion of pre-defined withdrawal treatment goal (e.g., planned detoxification/transition) as assessed by the Principal Investigator (after completion of the SOWS-Gossop and COWS).
- Concomitant medication assessment.
- Pill count and review of subject diary ([Appendix 3](#)) to measure compliance with previous day's doses.
- Vital Signs, including blood pressure and pulse at rest (sitting [or recumbent if necessary because of an AE]) and standing (if able) before an in-clinic dose of lofexidine and 3.5 hours after dosing on Days 8-13 and once before any dose on Day 14. Note that if subjects cannot stay in the clinic for measurement of the 3.5-hour post-dose vital signs required on Days 8-13, they will be given a portable digital blood pressure machine for measurement of their vital signs at this required time point. Subjects will also be provided a diary ([Appendix 3](#)) to record the measurements along with any symptoms of hypotension and/or bradycardia (see list in Section 13.2.2) the subject may have experienced.
- AE assessment.
- Clinical laboratory tests as clinically warranted.
- Complete physical examination as clinically warranted.
- C-SSRS (Since Last Visit Version; [Appendix 6](#)) before an in-clinic dose of lofexidine.
- A fingerprick blood sample will be collected during outpatient treatment when the subject reports to the clinic each day (before next scheduled dose) for analysis of plasma lofexidine concentration to monitor compliance.
- Qualitative urine drug screening (by on-site use of "dipsticks") will be done every day in an outpatient setting to monitor for illicit drug use.

#### **15.3.4 Study Discontinuation/End of Study**

Any subject that discontinues from the study, regardless of the reason (see all scenarios listed in Section 14.5.1), will be requested to complete all Study Discontinuation/End of Study assessments and procedures as listed below after the last dose of study medication.

- SOWS-Gossop.
- COWS.

- Completion of pre-defined withdrawal treatment goal (e.g., planned detoxification/transition) as assessed by the Principal Investigator (after completion of the SOWS-Gossop and COWS).
- Concomitant medication assessment.
- Pill count and review of subject diary ([Appendix 3](#)) to measure compliance with previous day's doses if not already performed.
- Vitals signs including blood pressure and pulse at rest (sitting [or recumbent if necessary because of an AE]) and standing (if able); respiration; and temperature.
- AE assessment.
- 12-lead ECGs (in duplicate) before the subject's last dose and 3.5 hours after dosing (or as close to this time as possible).
- Clinical laboratory tests.
- Complete physical examination (including body weight).
- Pregnancy test.
- Urine drug screen.
- C-SSRS (Since Last Visit version; [Appendix 6](#)).

### **15.3.5 30-Day Telephone Follow-up Contact**

A follow-up telephone contact will be attempted 30 days after the subject's last dose and will include an adverse event evaluation and an evaluation of the subject's current treatment status (e.g., relapse, current psychosocial treatment, successful entry into a methadone, buprenorphine or naltrexone program). Repeated attempts will be made to reach the subject (defined as a minimum of 3 telephone calls, followed by sending a letter). If repeated attempts are unsuccessful, this will be recorded in the subject's source document and eCRF.

## **15.4 Effectiveness Assessment Methods**

### **15.4.1 Assessment of Completion of Pre-Defined Withdrawal Treatment Goal**

The Principal Investigator will indicate if the subject has completed his/her pre-defined withdrawal treatment goal ([Appendix 4](#)) on Days 1-7 by responding to the following question: "Has the subject's withdrawal treatment goal been reached?" Note that, per protocol, subjects are required to continue on their dose of lofexidine through Day 7 even though the subject may have completed his/her withdrawal treatment goal before Day 7. This same assessment will be made at each visit during the 7 days of optional outpatient treatment (Days 8-14). This assessment should be completed after the SOWS-Gossop and COWS assessments.

### **15.4.2 Short Opiate Withdrawal Scale of Gossop (SOWS-Gossop)**

The SOWS-Gossop [16] will be completed by the subject at baseline, once daily at 3.5 hours ( $\pm$  10 minutes) after the first dose of study medication during in-clinic treatment and once

daily before an in-clinic dose of lofexidine during outpatient treatment. Note that at the time of each daily evaluation, subjects should consider their symptoms over the last 24-hour period or since the last time the subject took this test. Also, this scale should be completed before completion of the COWS.

The SOWS-Gossop scale assesses subjective symptoms of opioid withdrawal ([Appendix 1](#)). It is a subject-rated scale consisting of 10 items that are scored on a 4-point scale of 0 = none, 1 = mild, 2 = moderate, and 3 = severe (minimum score of 0, maximum score of 30) (see [Table 2](#) below). The overall score will be the simple sum of the 10-item scores. Lower observed values in SOWS-Gossop scores indicate a more positive clinical outcome.

Table 2. SOWS-Gossop Scoring Method

Condition	Score			
	None	Mild	Moderate	Severe
Feeling Sick	0	1	2	3
Stomach Cramps	0	1	2	3
Muscle Spasms/Twitching	0	1	2	3
Feeling of Coldness	0	1	2	3
Heart Pounding	0	1	2	3
Muscular Tension	0	1	2	3
Aches and Pains	0	1	2	3
Yawning	0	1	2	3
Runny Eyes	0	1	2	3
Insomnia/Problems Sleeping	0	1	2	3

Note: Possible score range = 0 to 30.

### 15.4.3 Clinical Opiate Withdrawal Scale (COWS)

The COWS [\[17\]](#) will be used to assess the effectiveness of lofexidine in alleviation of opioid withdrawal, and will be completed after the SOWS-Gossop and before the assessment of completion of pre-defined withdrawal treatment goal. It will be completed at baseline (before dosing on Day 1), once daily at 3.5 hours after the first dose of study medication during in-clinic treatment, and once daily before an in-clinic dose of lofexidine during outpatient treatment. The COWS is a clinician-administered instrument that rates 11 common opioid withdrawal signs and symptoms ([Appendix 2](#)). These include: resting pulse rate; sweating; restlessness; pupil size; bone or joint aches; runny nose or tearing; gastrointestinal (GI) upset; tremor; yawning; anxiety or irritability; and gooseflesh skin. The score for each item reflects the severity of the sign or symptom, and the total scores are grouped as mild (5-12 points), moderate (13-24 points), moderately severe (25-36 points), and severe (>36 points).

## 15.5 Safety Assessment Methods

### 15.5.1 Adverse Events

The occurrence of AEs will be assessed starting at the treatment phase of the protocol (i.e., with the first dose of study drug). Any AE that occurs during screening will be recorded in the subject's Medical History eCRF. The occurrence of Serious Adverse Events (SAEs) will be assessed after signing of the informed consent form.

Adverse events will be assessed and recorded around the same time each day by study staff during in-clinic lofexidine treatment. If an AE requires medical attention, it should be reported to a study physician immediately. A study physician or assigned staff must meet with the subject to assess all medical and psychiatric AEs reported by the subject, as well as those recorded by other study staff. Adverse events will be assessed by asking the subject, "How have you been feeling since I saw you last?" After current AEs are assessed, the study physician or assigned staff must review with the subject and assess any AEs unresolved from the previous day. For each daily AE assessment, details will be recorded in the subject's source document and AE eCRF, according to the procedures described in Section 16.7, the type of AE and whether it is serious (SAE) or non-serious, severity of each AE, and the relationship to the study agent. These categories are asking for the Principal Investigator or physician designee's best judgment of the severity and relatedness of each AE. The Principal Investigator or physician designee will also record, based on his/her best judgment, whether the AE is secondary to opioid withdrawal (see Section 15.5.1.1). In general, an AE should not be marked as withdrawal related AND related to study medication.

Any study subject with a related AE will be followed until the event is resolved to the satisfaction of the Principal Investigator and Sponsor's Medical Monitor. If the AE is unrelated, the subject will be followed until medically stable, and then will be referred, at the subject's sole expense, for ongoing care and/or treatment, which may include psychological and lifestyle counseling, support groups, or pharmacological and medical treatment.

During outpatient treatment, subjects will be queried about AEs at each daily clinic visit. All subjects will be instructed to contact the study physician or assigned staff if he or she experiences any symptoms of hypotension and/or bradycardia (see list in Section 13.2.2) (especially on standing from a sitting or lying position) and delay additional lofexidine dosing until further instructed.

All reported AEs will be recorded as described above.

#### **15.5.1.1 Withdrawal-Related Adverse Events**

The Principal Investigator or physician designee will also record, based on his/her best judgment, whether the AE is secondary to opioid withdrawal. Individual items reported on the efficacy scales (i.e., SOWS-Gossop, COWS) do not automatically qualify as a withdrawal-related AE unless the subject specifically reports them in response to the non-leading question (i.e., "How have you been feeling since I saw you last?"). In the event a subject reports "withdrawal" or a similar event encompassing a collection of potential withdrawal symptoms, the subject should be asked to elaborate so that each specific symptom can be recorded on the AE eCRF. In general, an AE/SAE should not be marked as withdrawal related AND related to study medication.

#### **15.5.2 Vital Signs**

Vital signs (sitting/standing systolic and diastolic blood pressure, pulse) will be measured at screening for all subjects.

During in-clinic treatment (Days 1-3 mandatory; Days 4-7 if subject receives all lofexidine doses in the clinic), resting (sitting [or recumbent if necessary because of an AE]) and standing (if able) systolic and diastolic blood pressure and pulse will be measured within 30 minutes before every dose and 3.5 hours ( $\pm 15$  minutes) after administration of study medication at 8 AM, 1 PM, and 6 PM; oral temperature and respiration before 8 AM dose only.

During outpatient treatment (Days 4-14) resting (sitting [or recumbent if necessary because of an AE]) and standing (if able) systolic and diastolic blood pressure and pulse will be measured before an in-clinic dose of lofexidine and 3.5 hours ( $\pm 30$  minutes) after dosing on Days 4-13 and once before any dose on Day 14. If the subject cannot stay in the clinic for measurement of the 3.5-hour post-dose vital signs required on Days 4-13, they will be given a portable digital blood pressure machine for measurement of their vital signs at this required time point and the values will be recorded in a subject diary ([Appendix 3](#)).

For the orthostatic vital sign (i.e., blood pressure and pulse) readings, subjects will remain at rest for 3 minutes before a vital sign reading, and then stand for 3 minutes before a second vital sign reading is taken. If a subject demonstrates potentially clinically significant vital signs (whether pre- or post-dose), as per the pre-defined criteria detailed in Sections [13.2.2](#) and [13.2.3](#), the event should be recorded on the subject's eCRF as an AE or SAE (see Sections [15.5.1](#), [16.7](#), and [16.8](#)) and the subject should be followed until medically stabilized to the satisfaction of the study physician.

Additionally, when the subject is experiencing blood pressure- or pulse-related symptoms (e.g., lightheaded, dizziness, palpitations), these should be recorded on the subject's eCRF as an AE or SAE (see Sections [15.5.1](#), [16.7](#), and [16.8](#)) even if the vital signs values do not meet the pre-defined criteria detailed in Sections [13.2.2](#) and [13.2.3](#).

### **15.5.3 12-Lead Electrocardiograms**

Using the ECG core lab-provided and validated instruments, baseline paper tracing 12-lead ECG (in duplicate) will be conducted on one day during the screening period at 8 AM (or as close to 8 AM as possible) and at 11:30 AM. Note that a time delay for the 8 AM ECG will not be considered a protocol deviation, but that the second ECG should be taken 3.5 hours after the first ECG. Duplicate 12-lead ECGs will also be conducted before the first dose on Day 1 at 8 AM and 3.5 hours ( $\pm 15$  minutes) after dosing; before the subject's last dose and 3.5 hours after dosing (or as close to this time as possible); or, if applicable, at discontinuation from the study. ECG intervals and abnormalities will be read centrally by a computer and confirmed by an individual accredited to read ECGs at the ECG core lab

. A qualified physician on site will evaluate tracings if there is a significant abnormality. The following intervals will be computed:

- Ventricular Rate      Number of R waves appearing within a 6-second period, multiplied by 10;
- PR Interval              Measured from the onset of the P wave to the onset of the QRS complex;

- QRS Complex      Measured from the beginning of the down stroke of the Q wave to the completion of the upstroke of the S wave;
- QT Interval      Measured from the beginning of the down stroke of the Q wave to the completion of the T wave;
- QTc (Bazett)      QT interval corrected for heart rate using Bazett's formula (QT/square root of RR);
- QTc (Fridericia)      QT interval corrected for heart rate using Fridericia's formula (QT/cube root of RR) (for safety monitoring/subject discontinuation purposes).

At screening (baseline assessment), a QTcF interval greater than 450 msec for males and greater than 470 msec for females will exclude the subject from study participation (see exclusion criterion #6 in Section [11.2.2](#)). In such cases, 2 additional ECGs should be taken at 10- to 15-minute intervals. The QTcF interval on all 3 ECGs should be confirmed by the Principal Investigator and if 2 of the 3 QTcF intervals exceed the gender-specific cut-off, then the subject should be judged a screen failure.

During the treatment phase of the study, when any QTcF interval exceeds 495 msec, 2 additional ECGs should be taken at 10- to 15-minute intervals. The QTcF interval on all 3 ECGs should be confirmed by the Principal Investigator. If it is determined that 2 of the 3 QTcF intervals exceed 500 msec or >25% above screen value, then the subject will be discontinued from the study.

Any time that 2 of the 3 QTcF measurements exceed 500 msec, contact the Sponsor's Medical Safety Monitor, to discuss the subject and the AE/SAE determination.

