-----------------------------------	--

Exclusion Criteria (continued)	
7. To avoid drug-drug interactions, subjects requiring the following will be excluded:
 
 
• tricyclic antidepressants, which may reduce the efficacy of imidazoline derivatives; and
 
• beta-receptor blockers, to avoid the risk of excessive bradycardia.
 

N	
Total enrollment will depend on subject drop-out rates. Approximately 250 to 500 subjects: enrollment will continue until a minimum total of 300 subjects (across this protocol and earlier lofexidine clinical studies expected to meet FDA safety database requirements) have been treated with clinically relevant doses of lofexidine for a minimum of 7 days. A target of at least 50 subjects each treated for clinical scenarios involving methadone or buprenorphine treatment will be enrolled (i.e., a total of 50 subjects receiving full or partial dose reduction from methadone, methadone-assisted withdrawal, and other methadone treatment scenarios and a total of 50 subjects receiving full or partial dose reduction from buprenorphine, transition to buprenorphine maintenance, and other buprenorphine treatment scenarios).

Safety Endpoints	
 
• Occurrence, seriousness, severity, and causality assessment of adverse events (AEs).
 
• Occurrence of AEs of special interest (i.e., orthostatic hypotension, orthostatic bradycardia, syncope).
 
• Occurrence of AEs not related to opioid withdrawal.
 
• Descriptive evaluation of vital signs (actual and change from baseline) for each time point.
 
• Descriptive evaluation of the three C-SSRS subscales (suicidal ideation, suicidal behavior, and intensity of suicidal ideation).
 
• Shifts from baseline in physical examination findings.
 
• Descriptive evaluation of clinical laboratory tests of hematology, chemistry, and urinalysis (actual and change from baseline).
 
• Descriptive evaluation of ECG (actual and change from baseline).
 

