### 11.2.2 Exclusion Criteria

Subjects who meet any of the following criteria will not be allowed to participate:

1. Be a female subject who is pregnant or lactating.
2. Have a very serious medical illness not under control as detailed below.
  - Serious medical illness will be determined at Screening by:
    - medical history;
    - physical examination;
    - 12-lead electrocardiogram (duplicate);

- clinical laboratory tests, including standard lab tests, an infectious disease panel for syphilis (subject is excluded if positive for active syphilis as per required laboratory tests; see also Section 15.5.4.2) and hepatitis (positive results do not exclude a prospective subject from participation unless there is an indication of active liver disease); and
- tuberculin test (purified protein derivative [PPD]) and/or a chest x-ray (a positive PPD result does not exclude a prospective subject from participation, but if diagnostic tests [e.g., chest x-ray] indicate that active disease is present, the subject will be excluded from participation; see also Section 15.5.4.2).
- Have active self-reported acquired immune deficiency syndrome (AIDS) or self-reported human immunodeficiency virus (HIV) positive status and taking retroviral medications currently or within the past 4 weeks.
- Have an unstable psychiatric condition (e.g., suicide risk, per Investigator judgment).

3. Current dependence (based on the M.I.N.I.) on any psychoactive substance (excluding caffeine, nicotine, and the subject's current opioid-dependence agent, which can include methadone and buprenorphine, for example, in agonist-maintained subjects) that requires detoxification or dose reduction as part of the pre-defined individual subject withdrawal treatment goal.
4. Have participated in an investigational drug study within the past 30 days.
5. Have history of lofexidine exposure in a prior clinical trial or otherwise.
6. Abnormal cardiovascular exam at screening, including any of the following:
  - clinically significant abnormal electrocardiogram (ECG) (e.g., second or third degree heart block, uncontrolled arrhythmia, or QTcF intervals greater than 450 msec for males and greater than 470 msec for females);
  - resting pulse less than 55 bpm or symptomatic bradycardia;
  - resting systolic blood pressure less than 95 mmHg or symptomatic hypotension;
  - resting diastolic blood pressure less than 65 mmHg;
  - resting blood pressure greater than 155/95 mmHg; or

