#### Resting (sitting [or recumbent if necessary because of an AE])

- Systolic blood pressure <90 mmHg and >20% below screen value;
- Diastolic blood pressure <50 mmHg and >20% below screen value;
- Pulse <50 bpm and >20% below screen value; or
- Symptoms of hypotension and/or bradycardia (e.g., lightheadedness, dizziness).

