### 13.2.3 Discontinuation Criteria

A subject will be discontinued from the study if any of the criteria listed below are met (see Section 10.4 for details on repeat confirmatory requirements). All instances should be recorded in the subject's source document and AE or SAE eCRF, as applicable.

- Resting systolic blood pressure <70 mmHg;
- Resting diastolic blood pressure <40 mmHg;
- Resting pulse <40 bpm;
- QTcF >500 msec or >25% above screen value for both males and females; or
- Syncope.

Additional discontinuation criteria based on cardiovascular events are:

- New onset of clinically significant abnormal ECG per Investigator judgment (e.g., second or third degree heart block or uncontrolled arrhythmia, prolonged QTcF interval).
- Persistent symptomatic hypotension (e.g., hypotension not responding to bed rest or fluids).
- Single occurrence of symptomatic bradycardia (as assessed by Principal Investigator/study physician/assigned staff, regardless of blood pressure) associated with chest pain, shortness of breath, or decreased level of consciousness.
- Persistent hypertension – resting blood pressure  $\geq 185/110$  mmHg recorded on 3 separate occasions taken at least 5 minutes apart AND within a 1-hour time period. If 2 of 3 readings are  $\geq 185/110$  mmHg (either systolic  $\geq 185$  mmHg or diastolic  $\geq 110$  mmHg) the subject must be discontinued.
- Medical Intervention for Cardiovascular Event: Any medical intervention (nonmedication or medication inclusive) used for the treatment of any cardiovascular event, with the exception of a positional intervention in subjects displaying hypotension.
- Any other clinically significant cardiovascular signs or symptoms that would place the subject at risk.
- Subject misses more than a total of 6 doses during Days 1-7.

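### The protocol's ECG ventricular rate (R waves in 6 seconds times 10) reads only in 10-bpm steps, which degrades individual values and spread in the descriptive ECG endpoint; define it from the measured RR interval instead.

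*Protocol*

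**What the plan says.** Protocol 15.5.3 lists the quantities to be computed from each ECG. Ventricular rate is the "Number of R waves appearing within a 6-second period, multiplied by 10". The section also says that "ECG intervals and abnormalities will be read centrally by a computer and confirmed by an individual accredited to read ECGs", and it defines QTcB and QTcF as QT divided by the square root and cube root of RR. RR is not itself on the list of computed quantities, and the section does not say how it is obtained.

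The Synopsis includes among the safety endpoints a "Descriptive evaluation of ECG (actual and change from baseline"). Protocol 17.1 and SAP 5.1 summarise continuous variables by mean, SD, minimum, quartiles and maximum. SAP 6.9 (ECG) sends the ECG analysis to a separate SAP and a stand-alone report, which are not among the documents.

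ECGs are taken in duplicate at screening, before and 3.5 hours after the first dose on Day 1, and around the last dose. Neither document says how the two tracings of a pair are combined.

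The numerical limits on slow rate are written on pulse: "resting pulse less than 55 bpm or symptomatic bradycardia" excludes at screening (11.2.2), "Pulse <50 bpm and >20% below screen value" holds a dose (13.2.2), and "Resting pulse <40 bpm" discontinues (13.2.3).

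**The concern.** One extra R wave in a 6-second window is worth 10 bpm, so a true rate between two multiples of 10 is reported as one or the other according to where the window happens to fall. Section 15.5.3 thus specifies a coarse bedside count for tracings that are read by computer, and for which RR is needed anyway.

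Safety is the primary objective, and the protocol itself recognises a bradycardia risk in its beta-blocker exclusion. Actual ECG rate and its change from baseline form part of a listed safety endpoint. Each subject has few on-treatment ECGs, so there is little averaging to absorb the rounding. At stake is the quality of subject-level and distributional ECG rate results, not the trial's real-time monitoring of slow pulse.

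**Working it through.** The plan gives no figure for the precision of ECG rate, so there is nothing of its own to reproduce.

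**Inputs from the documents.** The rate definition and duplicate recording (15.5.3), and enrolment of about 250 to 500 (10.2).

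**Assumptions not in the documents.** A regular rhythm, a window start that is random relative to the beats, and independent windows for the tracings compared or averaged.

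**Distribution of one reading.** For a true rate HR, let k be the whole part of HR/10 and f the fractional part. The reading is 10k with probability 1 − f and 10(k + 1) with probability f. Its mean is 10(k + f) = HR, so it is unbiased. Its SD is 10 × √[f(1 − f)], at most 5 bpm (at f = 0.5).

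- True 48: reads 40 with probability 0.2 and 50 with probability 0.8.
- True 45: reads 40 or 50 with probability 0.5 each.
- True 54: reads 50 with probability 0.6 and 60 with probability 0.4.

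**Error across subjects.** With f spread evenly over 0 to 1, the average of f(1 − f) is 1/6.

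- Per tracing: SD = 10 × √(1/6) = 4.08 bpm.
- Change from baseline, single tracings: 4.08 × √2 = 5.77 bpm.
- Change from baseline, duplicate means: 5.77/√2 = 4.08 bpm.

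A simulation of 400,000 subjects, with an assumed baseline of 72 bpm (SD 10) and a true fall of 10 bpm, gave 4.08, 5.78 and 4.08 bpm, with a mean change of −10.0.

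**Group means.** The added standard error is the change-score SD divided by √n.

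| | n = 250 | n = 500 |
|---|---|---|
| Single tracings | 5.77/√250 = 0.37 bpm | 5.77/√500 = 0.26 bpm |
| Duplicate means | 4.08/√250 = 0.26 bpm | 4.08/√500 = 0.18 bpm |

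**Individual changes.** In the same simulation with single tracings, the readings showed no slowing at all in 50% of subjects after a true 5-bpm fall, in 17% after a 10-bpm fall and in 2% after a 15-bpm fall.

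**Categories, if any were used.** A true 48 bpm would be classed below 50 in 20% of single readings. For the mean of two tracings it would be 1 − 0.8² = 36%. The documents define no ECG rate category; this only shows what one would inherit.

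**If the window starts on an R wave.** The reading is then no longer unbiased in level. A true 48 always reads 50 and a true 54 always reads 60, so actual values are pushed upward. The 10-bpm step remains.

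**The case against.** The strongest reply is that the trial does not watch for slowing with this variable. A reader might infer from the 10-bpm step that the trial cannot detect the bradycardia it monitors. The documents do not support that. The limits of 55, 50 and 40 bpm are all on pulse, a vital sign measured 7 times a day in clinic, or 7 × 3 = 21 time points over Days 1-3. Section 10.4 speaks of heart rate, but it points to 13.2.2 and 13.2.3, where the limits are on pulse. No numerical hold or discontinuation rule uses ECG ventricular rate; the numerical ECG rule is on QTcF. SAP 6.9 tabulates the pulse criteria and plots mean pulse separately. The 20% criterion also exceeds one step: for screening pulses of 55 to 80 it is 11 to 16 bpm. This part of the objection stands in full.

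A reader might also infer that the rounding carries into QTcF, because RR is not among the listed quantities while the coarse rate is. Were RR taken from the count, a QT of 440 msec at a true 55 bpm (QTcF 427 msec) would come out as 414 or 440 msec. But 15.5.3 nowhere derives RR from the count, and its computer reading of intervals suggests otherwise. This is a line to clarify, not an error shown.

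It is fair, too, that the endpoint is descriptive, that mean change is barely affected, and that the unseen ECG SAP may already define rate differently. Those facts make the point small. They do not remove it: the endpoint is also summarised by SD, quartiles and extremes, and 15.5.3 holds the only definition available.

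**Conclusion.** The point holds in a limited form, at low priority. The stated definition of ECG ventricular rate is needlessly coarse for a computer-read core-lab ECG. It adds an error SD of about 4.1 bpm per tracing, and about 5.8 bpm (single tracings) or 4.1 bpm (duplicate means) per change from baseline. Individual values, SDs, percentiles, extremes and any rate categories are degraded. Group mean change is not biased and loses only about 0.2 to 0.4 bpm of standard error at 250 to 500 subjects. The pulse-based exclusion, dose-hold and discontinuation rules are untouched, and no QTcF error is shown.

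These sizes rest on a regular rhythm, a random window start and independent windows. The percentages for individual falls also use the assumed baseline of 72 bpm (SD 10).

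**What to change.** In Protocol 15.5.3 and the separate ECG SAP, define ventricular rate as 60 divided by the mean RR interval in seconds from the core-lab computer reading, averaged over the duplicate tracings. State that QTcB and QTcF use that measured RR. Use this rate for the actual-value and change-from-baseline ECG summaries and for any rate categories.

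The cost is one line in each document. RR is already required for both QT corrections, so no new data are needed and no clinical rule changes. If the core lab already works this way, the edit simply brings the protocol wording into line with practice.
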